*Two-stage single-arm phase II designs:* There are many two-stage designs that meet nominal Type I and II Error criteria. We choose a two-stage design with a slightly increased expected sample size (EN) of 25.6 but keeps the two-stage sample size below that of a single-stage study ( $n=42$ ) as follows: In stage I, 17 patients are accrued and the study is stopped only if 7 or fewer patients experience a complete remission (CR). Stopping in this fashion is interpreted as evidence of futility. If 8 or more patients experience a CR, the study continues to accrue an additional 24 participants (for a total of 41). At the end, the study is said to generate evidence in support of the hypothesis that incorporating Vosaroxin into frontline AML induction chemotherapy is worthy of future study if 22 or more patients experience CR (i.e. if the observed response rate is greater than 53%). If frontline induction therapy with Vosaroxin plus standard dose continuous infusion cytarabine fails to improve upon the historical CR rate of 40% with conventional 7+3 induction therapy, the study has a 64% probability of early termination (PET).

A standard (frequentist) two-stage design is unable to handle deviations from its planned design (i.e., when the sample size is anything other than 17 or 41). This occasionally happens in multi-center clinical trials for practical reasons relating to the speed of communication and clinical expediency. Green and Dahlberg introduced flexible designs to that are able to accommodate such deviations from planned designs with minimal impact to their nominal operating characteristics. However, in this case, the Green and Dahlberg criteria result in a 25% PET, which poorly protects patients from ineffective therapy. This is one motivating factor in our choice of employing a likelihood-based assessment of the evidence. The likelihood ratio reveals alternative interim stopping criteria that maintain nominal Type I and Type II Error rates, adding significant logistic flexibility (Table 6). Within the context of standard two-stage design, we believe our proposed design best balances the probability of early termination and expected sample size under the stated constraints.

**Table 6.** Interim stopping rules that are constrained to lie between 30% and 60% of total accrual and have a probability of early termination that exceeds 50%. Type I & II Error rates are below designed nominal levels (5% & 20%).

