Observed CRs in stage I	Stage I sample size	Probability of early termination	Expected sample size	Likelihood ratio favoring null that corresponds to Simon's futility stopping rule
7	17	64%	25.6	1/3.375
8	19	67%	26.3	1/3.375
9	21	69%	27.2	1/3.375
10	23	71%	28.2	1/3.375
6	16	53%	27.8	1/5.062
7	18	56%	28.2	1/5.062
8	20	60%	28.5	1/5.062

*Likelihood assessment of evidence:* In accordance with our desire to maintain a uniform study design, we set a total sample size of 41 participants, a 17 patient first stage, and an interim futility criterion of 7 or fewer CRs with the added flexibility at the interim analysis indicated in table 1. The interim futility criterion translates to stopping the study at the end of the first stage if the observed likelihood ratio is less than 1/3.375 (i.e., if the evidence better supports the null hypothesis by a factor of at least 3.375). The likelihood ratio is defined as  $LR = \theta_1^r (1 - \theta_1)^{n-r} / \theta_0^r (1 - \theta_0)^{n-r}$  where  $r$  is the number of CR's among  $n$  patients treated and  $H_0: \theta = \theta_0 = 0.4$ ,  $H_1: \theta = \theta_1 = 0.6$ . The translated stopping LR's for the competing designs are listed in the last column of table 1.

An important aspect of the likelihood assessment is that it can quantify the reliability of an observed outcome. For example, while the study would stop early with either an observed LR of 1/3.375 or 1/15 (evidence favoring the null hypothesis), the associated false discovery rates of 0.23 (=1/4.375) and 0.063 (=1/16), respectively, distinguish between those results and provide critical information for investigators when interpreting this evidence at the end of the study.

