LR Class	Trials at end of two-stage design	Weak evidence	Add 10 patients	Weak evidence	Add 10 patients	Weak evidence
$LR \leq 1/3.375$	1145		207		105	
$1/3.375 < LR < 1$	260	424 (8.5%)	113	179 (3.6%)	35	58 (1.2%)
$1 < LR < 3.375$	164		66		23	
$LR \geq 3.375$	247		38		16	
Results under true Ha:						
$LR \leq 1/3.375$	143		39		16	
$1/3.375 < LR < 1$	148	397 (7.9%)	48	135 (2.7%)	30	134 (1.1%)
$1 < LR < 3.375$	249		87		26	
$LR \geq 3.375$	4026		223		63	

a 64% (3184) and 8.7% (434) trials stopped early for futility under the true null and true alternative hypotheses, respectively.

Under the likelihood evidentiary paradigm observed results are reported as follows (let  $K > 1$  be the pre-specified LR that maintains a certain false discovery rate): 1) sufficiently strong evidence for the null ( $LR \leq 1/K$ ); 2) actionable weak evidence for the null ( $1/K < LR < 1$ ); 3) actionable weak evidence for the alternative ( $1 < LR < K$ ); 4) sufficiently strong evidence for the alternative ( $LR \geq 1/K$ ). We will also report the FDR for the result at hand, i.e.  $1/(LR+1)$ . As detailed below, this trial may recruit additional participants if the observed LR is weak (i.e.,  $1/K < LR < K$ ) with a maximum of 61 participants.

A significant number (~8%) of discoveries under the null and alternate hypotheses for our two-stage design had LR of exactly 3.375. Though such results would allow the conclusion of sufficient activity to warrant further investigation in more definitive trials because it passes nominal Type I and II Error rate criteria, we propose to further evaluate these results in the extension cohorts by setting  $K=4$ , treating those trials with LR's of 3.375 as weak evidence. The PET remains unaffected by this slight change. However, the design that uses  $K=4$  and a total sample size of 61 patients has a false positive rate that decreases to 3.7% and power that increases to 83.7%. This strategy also decreases the false discovery rate to 3.9% (table 8). Hence such a design is quite feasible.

**Table 8.** Simulation results for extending the likelihood two stage trial for the purpose of refining weak evidence for K=4. Cells contain the number (proportion of 5000) trials in each evidentiary class.

Results Under True Ho:						
LR Class	Trials at end of two-stage design	Weak evidence	Add 10 patients	Weak evidence	Add 10 patients	Weak evidence

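### Seven or fewer CRs in 17 is evaluated as a definite stop in Section 12.3 but operated as a DSMB review elsewhere, so PET 64% is an upper limit and EN 25.6 a lower limit

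*Combined protocol and SAP*

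**What the plan says.** Section 12.3 treats the interim result as decisive. It says "The interim futility criterion translates to stopping the study at the end of the first stage" when the likelihood ratio (LR) falls to the threshold, and illustrates the point by saying that "the study would stop early with either an observed LR of 1/3.375 or 1/15". An LR of 1/3.375 is what 7 CRs in 17 gives. The section says that, if the regimen does not improve on 40%, "the study has a 64% probability of early termination (PET"), and it describes the design as having a "slightly increased expected sample size (EN) of 25.6". The footnotes to Tables 7 and 8 count 3184 null trials and 434 alternative trials of 5000 each as "trials stopped early for futility under the true null and true alternative hypotheses, respectively". For the stricter K=4 version it adds: "The PET remains unaffected by this slight change".

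PET is also the ground on which the design was chosen. Table 6 is restricted to rules that "have a probability of early termination that exceeds 50" per cent, and a flexible design is set aside because its criteria "result in a 25% PET, which poorly protects patients from ineffective therapy".

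The operating text differs. The Synopsis (Study Design and Statistical Plan), Section 3.1 and Section 12.2 all say that at seven or fewer CRs a DSMB looks at the data and decides whether enrolment should go on. Only the result above seven has an automatic consequence, which is to continue to 41. Section 13.1.5 repeats the DSMB's general remit without naming a threshold.

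**The concern.** The two descriptions are different rules. If the DSMB can continue after 7/17 or fewer, PET and EN depend on how often it does so, and the plan gives neither a criterion nor a probability for that. The figures in 12.3 then describe the case in which the DSMB always stops.

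At stake is mainly the accuracy of the patient-protection claim. PET is the plan's own selection criterion, and a reader would take 64% as a property of the trial as it will be run. A smaller matter is the Table 6 caption, which puts Type I error below 5%: for the 7/17 rule that also depends on the stop being mostly followed.

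**Working it through.** **Inputs.** Null and alternative CR rates 0.40 and 0.60; stage 1 n = 17 with futility at 7 or fewer; total 41 (17 + 24); success at 22 or more CRs; LR = 1.5^(2r−n) from the formula in 12.3; extensions to 51 and then 61 while 1/K < LR < K. All are from Section 12.3. The probability that the DSMB continues is not in the documents, so it is an assumption shown over its range.

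**Reproducing the plan's figures with a definite stop.**
- PET = P(X ≤ 7 | 17, 0.4) = 0.6405 (stated 64%).
- EN = 17 + 24 × (1 − 0.6405) = 25.63 (stated 25.6).
- LR at 7/17 = 1.5^(−3) = 1/3.375.
- Type I error at 22 or more of 41 = 0.0473; power = 0.8009 (stated 80%).

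**The simulation tables make the same assumption.** The stopped trials and the four LR classes at the end of stage 2 exhaust all 5000 trials, so no trial at or below 7/17 continues:
- Table 7 null: 1145 + 260 + 164 + 247 + 3184 = 5000.
- Table 7 alternative: 143 + 148 + 249 + 4026 + 434 = 5000.
- Table 8 null: 878 + 527 + 286 + 125 + 3184 = 5000.
- Table 8 alternative: 65 + 226 + 607 + 3668 + 434 = 5000.

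**PET and EN under the null when the DSMB may continue (41 patients, no extension).** If it continues in a share w of results at or below 7/17, whatever the count, PET = 0.6405 × (1 − w) and EN = 17 + 24 × (1 − PET).

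| DSMB behaviour | PET | EN |
|---|---|---|
| w = 0 (always stops) | 64.1% | 25.6 |
| w = 0.25 | 48.0% | 29.5 |
| w = 0.5 | 32.0% | 33.3 |
| w = 1 (never stops) | 0% | 41 |
| continues only at exactly 7/17 | 44.8% | 30.3 |

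The last row uses P(X = 7 | 17, 0.4) = 0.1927, which is 30.1% of the null probability at or below 7: PET = 0.6405 − 0.1927 = 0.4478.

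Share at which PET reaches Table 6's 50% screen: 1 − 0.50/0.6405 = 22%. Share at which it reaches the rejected design's 25%: 1 − 0.25/0.6405 = 61%.

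**Error rates.** Exact binomial at 41 patients; exact convolution through 51 and 61 for the extensions.

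| Design | Measure | Always stopped | Continued only at 7/17 | Never stopped |
|---|---|---|---|---|
| 22 or more of 41, no extension | Type I | 4.73% | 5.15% | 5.32% |
| | Power | 80.1% | 82.9% | 83.9% |
| K=4, extended to 61 | Type I | 3.45% | 3.76% | 3.90% |
| | Power | 83.6% | 87.3% | 88.9% |
| K=3.375, extended to 61 | Type I | 5.83% | 6.48% | 6.79% |
| | Power | 86.0% | 90.0% | 91.7% |

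At 41 patients, with overrides that ignore the count, Type I error passes 5% once the DSMB stops in fewer than about 55% of cases.

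**EN with extensions.** With the rule always followed, null EN is 28.1 for K=4 and 26.7 for K=3.375, so 25.6 applies only to the design that ends at 41.

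**The case against.** The strongest reply is that advisory futility review is ordinary practice and is the sponsor's choice. The Synopsis, 3.1 and 12.2 agree with one another on conduct, and the first statement of the rule in 12.3 makes seven or fewer CRs a necessary condition for stopping, which is compatible with discretion. The practice is indeed acceptable, and the defect is one of labelling. But the later sentences of 12.3 and the simulation tables leave no discretion, so the inconsistency remains.

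It is also fair that the size rests on an assumed override share and that a DSMB would look at the count. At exactly 7/17 the chance of still reaching 22 of 41 is 2.2% under the null and 48.9% under the alternative, so a share that ignores the count is only illustrative. That is why limits are given rather than a single corrected figure.

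Four stronger inferences are tempting, and the documents do not support them:
- **That the design loses its advantage over the rejected one.** The 44.8% example breaks only the 50% screen and is still well above 25%. Reaching 25% takes about 61% overrides. The comparison would also be uneven, since discretion would be applied to the chosen rule and not to the rejected one.
- **That all of Tables 6 to 8 rest on 7/17.** Only row 1 of Table 6 is that rule; its other rows are alternative interim sizes.
- **That Section 13.1.5 itself sets a discretionary 7/17 rule.** It names no threshold.
- **That the stated 3.7% false positive rate for K=4 shows an override effect.** Table 8 gives (125 + 32 + 15)/5000 = 3.44%, which agrees with the exact always-stopped 3.45%. The 3.7% is a separate discrepancy.

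**Conclusion.** The inconsistency is real and should be corrected. PET 64% and EN 25.6 are correct calculations for a definite stop, which the operating text does not impose. As operated, PET under a 40% CR rate lies between 0% and 64%, and EN for the 41-patient design without extension lies between 25.6 and 41. The favourable ends are reached only if the DSMB always stops. A modest degree of discretion, about 22% overrides or always continuing at exactly 7/17, is enough to fall below the plan's 50% screen.

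A reader might infer that discretion seriously inflates the false positive rate or undermines the trial's conclusion. It does not. At 22 or more of 41, Type I error rises by at most 0.59 percentage points (5.32 − 4.73), just past the nominal 5%. With K=4 it stays below 4%, and power never falls. The Table 6 caption is affected only to that extent for the 7/17 rule. These limits are exact under the plan's own rates of 40% and 60%. The override share is unknown.

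**What to change.** Reconcile Section 12.3 and its tables with the Synopsis, 3.1 and 12.2.

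**Preferred, with no change to conduct.** State in 12.3 that:
- the interim futility rule is non-binding;
- for the 41-patient design without extension, PET 64% is an upper limit and EN 25.6 a lower limit under the null, reached only if the rule is always followed;
- if the rule is never followed, Type I error and power are at most 5.3% and 83.9% at 22 or more of 41, 3.9% and 88.9% with the K=4 extension to 61, and 6.8% and 91.7% with the K=3.375 extension to 61.

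Label the PET and EN columns of Table 6, its Type I error caption, and the footnotes to Tables 7 and 8 as holding if the futility rule is always followed. If EN is quoted for the extension designs, use 28.1 (K=4) and 26.7 (K=3.375) under the null with the rule always followed. The caption needs one further check: at 22 or more of 41, the 7/18 and 8/20 rows give 5.003% and 5.03% even when always stopped, so the label alone does not make it exact for those two rows.

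The cost is one statement and a few labels. The sponsor would then be reporting PET and EN as limits and Type I error as up to 5.3% at 41 patients.

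**Alternative.** State in both Synopsis sections, 3.1 and 12.2 that seven or fewer CRs in the first 17 evaluable patients ends enrolment, and align 13.1.5 if wished. The stated PET and EN then stand. This removes a DSMB decision, so it is a substantive amendment needing IRB approval under Section 13.1.2.

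The 3.7% against Table 8's 3.44% should be corrected separately; neither option resolves it.

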## 3. STUDY DESIGN

### 3.1. Overall Design and Plan

- Single-arm, open-label, phase II study of vosaroxin in combination with cytarabine in patients with newly diagnosed AML.
- Vosaroxin will be administered intravenously at 90 mg/m^2 on days 1 and 4. Cytarabine will be administered in standard fashion as a continuous infusion of 100 mg/m^2 daily on days 1-7.
  - Patients with evidence of residual leukemia on “Day 14 biopsy” following initial induction will be offered re-induction with intravenous vosaroxin at 70 mg/m^2 on days 1 and 4 in combination with continuous infusion cytarabine at 100 mg/m^2 daily on days 1-7.
- Two-stage design. Forty-one (41) patients will provide 80% power to detect a 20% increase in complete remission rates (from 40% to 60%) with a Type I Error rate of 5%. The design permits one interim look to examine evidence of futility after the first 17 patients are evaluable for response. If  $\leq 7$  patients achieve CR then the likelihood of reaching the goal endpoint of  $\geq 60\%$  remission would be diminished. In this case, the DSMB (consisting of a representative from the funding organization, the study chairs, a biostatistician, and participating investigator to be selected by the study chairs) will review the clinical data to determine the merits of continued enrollment. If  $> 7$  CRs are observed then the second stage will open automatically and increase enrollment to 41 patients.
  - Stage 1: First 17 patients who are evaluable for response prior to futility analysis
  - Stage 2: Patients 18-41 enrolled after futility analysis
- Likelihood-based assessment of the statistical evidence be used to determine the reliability of the data generated and will provide the option of adding one or two extension cohorts of 10 participants each if the initial trial results are inconclusive.

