With a likelihood design, it can happen that the trial yields weak or inconclusive evidence. Technically this can happen in all standard (i.e., frequentist) two-stage designs as well, but when it does the standard design forces a ‘call’ of either ‘Reject the null’ or ‘Fail to reject the null’ (the assignment depends on how the Type I Error is spent throughout the study and can lead to some uncomfortable circumstances, such as calling evidence supporting the alternative as ‘Fail to reject’ and vice versa). Hence, in likelihood designs, it is desirable to minimize the chance of observing weak evidence. Our proposed two-stage design accomplished this sufficiently, as we next describe, but the important thing to remember is that if the trial does result in weak evidence there is no penalty for accruing additional subjects and reporting the combined evidence (assuming that resources will allow such action). In a likelihood design, the probability of weak evidence is driven to zero by the sample size, so it is always possible to refine inconclusive results, often within limited resource constraints.

Table 7 displays a simulation of the proposed trial, potential outcomes, and their probability of occurrence. Analytic expressions for these probabilities exist, but simulating is simpler and essentially as accurate. Table 2 shows what we expect to happen, on average, for our proposed design and what happens if the sponsor chooses to add patients at the end of the trial to refine weak evidence (if observed). In particular, it shows that the chance of observing weak evidence at the end of the study is ~8%, which can be reduced to ~3% (or ~1%) by adding 10 (or 20) more participants. Importantly, only an additional 54 false positives were observed, which represents a very modest inflation in the Type I Error rate from 4.9% (=247/5000) to 6%, and 286 trials under the alternative achieved sufficient evidence to declare efficacy for an increase in power from 80% (=4026/5000) to 86%. At the end of stage II, the false discovery rate for any type of rejection (i.e., any likelihood ratio greater than or equal to 3.375) is 5.8% (=247/(247+4026)). Clearly, cohort expansion can proceed with minimal rates of unwanted consequences.

**Table 7.** Simulation results for extending the likelihood two stage trial for the purpose of refining weak evidence. Cells contain the number (proportion of 5000) trials in each evidentiary class.

Results Under True Ho:						

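### Section 12.3 prints the reporting class for strong evidence favouring the alternative as LR ≥ 1/K where LR ≥ K is meant, so the class overlaps the weak-evidence classes

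*Combined protocol and SAP*

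**What the plan says.** After Table 7, section 12.3 introduces a prespecified K > 1 and sets out how results will be reported:

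- Class 1, "1) sufficiently strong evidence for the null": LR ≤ 1/K.
- Class 2, weak evidence for the null: 1/K < LR < 1.
- Class 3, "3) actionable weak evidence for the alternative": 1 < LR < K.
- Class 4, "4) sufficiently strong evidence for the alternative": printed as LR ≥ 1/K.

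The same paragraph then says "this trial may recruit additional participants if the observed LR is weak", defines weak as 1/K < LR < K, and caps the trial at 61 patients. The next paragraph proposes K = 4, "treating those trials with LR's of 3.375 as weak evidence".

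Elsewhere in section 12.3 a rejection is "any likelihood ratio greater than or equal to 3.375". The strong row for the alternative is LR ≥ 3.375 in Table 7 and LR ≥ 4 in Table 8. Section 12.3 also gives the success rule as a count: 22 or more CRs in 41. The synopsis statistical plan and section 12.2 single out the same count.

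**The concern.** Classes 1 and 4 should mirror each other. Because K > 1, the printed condition for class 4 takes in all of classes 2 and 3, and it meets class 1 at LR = 1/K. The four classes therefore do not partition the possible results. A result between 1/K and K carries two labels: weak, with the option to extend, and strong for the alternative. A prespecified rule should not leave the choice between those labels open until the data have been seen. The list is also the plan's only general statement, in terms of K, of what counts as strong evidence for activity.

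**Working it through.** **Inputs.** The rates are 0.40 and 0.60 (section 3.1: "to detect a 20% increase in complete remission rates (from 40% to 60%) with a Type I Error rate of 5" per cent). From section 12.3 come the likelihood-ratio formula, the stage 1 stop at 7 or fewer CRs in 17, the total of 41, and K = 3.375 (Table 7) or K = 4 (Table 8).

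**Likelihood ratio.** With r CRs in n patients, LR = (0.6/0.4)^r × (0.4/0.6)^(n−r) = 1.5^(2r−n). At 22 of 41 this is 1.5³ = 27/8 = 3.375, the plan's own value.

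**Reproducing the plan.** Exact two-stage binomial enumeration (stop at ≤ 7/17, otherwise continue to 41, success at ≥ 22) gives:

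- probability of early termination under the null 64.1% (plan: 64%);
- expected sample size 17 + 24 × (1 − 0.6405) = 25.6 (plan: 25.6);
- type I error 4.73% (plan: 247/5000 = 4.9%; the simulation standard error is √(0.0473 × 0.9527/5000) = 0.3 percentage points);
- power 80.1% (plan: 80%).

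**Classing results at 41 patients with K = 4, so 1/K = 0.25.**

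| CRs of 41 | LR | Among classes 1–3 | Class 4 as printed (LR ≥ 0.25) | LR ≥ 4 |
|---|---|---|---|---|
| 18 | 1.5^−5 = 0.132 | 1 | no | no |
| 19 | 1.5^−3 = 0.296 | 2 | yes | no |
| 20 | 1.5^−1 = 0.667 | 2 | yes | no |
| 21 | 1.5 | 3 | yes | no |
| 22 | 3.375 | 3 | yes | no |
| 23 | 1.5^5 = 7.594 | none | yes | yes |

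At 19 of 41 the false discovery rate that the plan would report beside the label, 1/(LR + 1), is 1/1.296 = 0.77.

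With K = 3.375 the double labels fall on 20 and 21 of 41 (weak and strong). At 19 of 41, LR equals 1/K exactly, so that result sits in classes 1 and 4 together. A count of 22 is then correctly strong.

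**Probability of class 4 at 41 patients, K = 4.**

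| True CR rate | As printed (≥ 19 CRs), exact | LR ≥ 4 (≥ 23 CRs), exact | As printed, Table 8 counts | LR ≥ 4, Table 8 counts |
|---|---|---|---|---|
| 40% | 17.9% | 2.5% | (527 + 286 + 125)/5000 = 18.8% | 125/5000 = 2.5% |
| 60% | 89.7% | 72.6% | (226 + 607 + 3668)/5000 = 90.0% | 3668/5000 = 73.4% |

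The strong row of Table 8 agrees with the exact probabilities for LR ≥ 4, so the simulated rule was LR ≥ K and not the printed one.

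**The case against.** The strongest reply is that the slip corrects itself. Class 3 stops at K, the weak zone stops at K, and the rejection rule and both tables use LR ≥ K, so only one reading of class 4 is coherent. The list governs how results are reported, while the success rule is stated separately as 22 CRs; 19 to 21 of 41 cannot meet that rule whatever class 4 says. This stands. It makes misuse unlikely and settles that the point is minor. It does not make the printed condition right.

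Four stronger readings may tempt a reader, and the documents do not support them:

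- **That 19 to 22 of 41 are reclassified as strong.** They gain a second label; classes 2 and 3 still hold them. For 22 of 41 the label is wrong only under K = 4. It is strong under K = 3.375 and a success under the 22-CR rule.
- **That a futility result of 7 of 17 could become an efficacy claim.** Its LR is also 0.296, and adding its null probability to the literal class would give 17.85% + 19.27% = 37.12%. But 7 of 17 is governed by the futility rule: section 12.3 treats it as futility, and the synopsis and sections 3.1 and 12.2 send it to the DSMB. Nothing leads from there to a claim of activity.
- **That the extension rule loses its meaning.** It has its own explicit interval, 1/K < LR < K, and does not depend on class 4.
- **That the trial's false positive rate is 18%.** That would be the rate of a rule the plan did not simulate and uses nowhere else.

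**Conclusion.** The condition printed for class 4 is wrong and should read LR ≥ K. Taken literally with K = 4, it gives two labels to 19, 20 and 21 of 41, and to 22 of 41 under that K only. Its probability at 41 patients under a 40% rate would be 17.9% exact (18.8% from the Table 8 counts) instead of 2.5%. These figures assume K = 4, a stop whenever 7 or fewer of the first 17 respond, and a literal reading of the list. They show the size of the contradiction, not a property of the design. The stated type I error, power, sample size, futility rule and extension interval do not change. Severity: a minor but real correction to a prespecified threshold.

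**What to change.** In the list of reporting classes in section 12.3, change class 4 to LR ≥ K. This costs one symbol and has no effect on the design.

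Printing counts would prevent misreading, but each set must name its K:

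- K = 4, strong for the alternative: ≥ 23/41, ≥ 28/51, ≥ 33/61. Strong for the null: ≤ 18/41, ≤ 23/51, ≤ 28/61. Weak in between.
- K = 3.375, strong for the alternative: ≥ 22/41.

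The K = 4 counts make 22 of 41 weak, while section 12.3 counts 22 CRs as success and the synopsis and section 12.2 single out that count. If the counts are added, one sentence must say how the K = 4 class relates to the 22-CR rule, for example whether 22 of 41 is reported as a success, as weak evidence eligible for extension, or as both in a stated order. The symbol change alone does not settle that question and should not appear to.
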